Ketamine is a well-known analgesic that has been frequently used pre-, intra-, and post-operatively. The analgesic property of ketamine is dose dependent, but it is generally believed to be short lived, as the medication is metabolized within an hour.⁷ Although ketamine has been shown in animal studies to block central sensitization to mediate long-acting analgesia,⁸ this remains to be proven in clinical practices.⁹ Low dose ketamine (<0.5mg/kg/hr) is used routinely and safely for inpatient pain management¹⁰ and outpatient management of certain chronic neuropathic pain conditions such as complex regional pain syndrome.¹¹

Meanwhile, in the last ten years or so, a number of studies have provided exciting evidence that ketamine has rapid-onset antidepressant effects that may last up to seven days.^{12-14,15,16} Several mechanisms have been proposed to explain this mood elevating effect of ketamine including increased glutamate transmission^{17,18} and increased brain derived neurotrophic factor expression.¹⁹ Animal studies have confirmed that ketamine, given as an analgesic, has rapid and

enduring mood elevating effects in postoperative pain states.²⁰ Despite its wide use in the postoperative setting as an analgesic, however, few clinical studies have examined the effect of ketamine on mood and functional status in the postoperative patients. Currently, there is only one study on peri-operative use of ketamine in bariatric patients,²¹ which showed that pre-inductive use of ketamine leads to early extubation and decreased total use of opioids. No study, in contrast, has examined the effects on mood and functional recovery with the use of ketamine postoperatively for pain control.

A number of pro- and anti-inflammatory cytokines (interleukin IL-1, IL-2, IL-6, IL-8, IL-10, IL-12, and tissue necrosis factor, TNF- α) have been linked with stress and mood regulation.²² Some of these cytokines, particularly IL-1, IL-6 and TNF- α , have also been implicated in pain states as well. In addition, reduced serum levels of brain derived neurotrophic factor (BDNF) have been described to correlate with pain as well as depressed mood, and ketamine has been hypothesized to increase BDNF levels.²³ However, there has been limited study in postoperative pain on the involvement of cytokines and neurotrophic factors as potential markers for assessing pain and predicting analgesia.

Study Rationale

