Ketamine, given for postoperative pain control, can be hypothesized to have long lasting analgesic effects as well as effects on improving mood and function in the postoperative period. Ketamine can be administered as a single dose in the post-anesthetic care unit (PACU), where patients are closely monitored for potential side effects. We hypothesize that postoperative use of ketamine should lead to improvement in pain indices including visual analog scale (VAS), a decrease in opioid requirement, mood improvements as measured by psychometric indices, and finally improvements in functional measures including early mobility and faster discharge from the hospital. In addition, we will assess serum levels of IL-1, 6, TNF- α , and BDNF to see if alterations in levels of cytokines and neurotrophic factors occur with postoperative pain and how ketamine treatment may influence the levels of these biomarkers.

Study Objective

Specific aim 1: examine the effect of a single, subanesthetic dose (0.4mg/kg) of ketamine vs. saline control on mood and postoperative function in patients who have undergone gastric bypass and sleeve gastrectomies.

Pain relief and changes in postoperative mood and function will be assessed using both patient report, in the forms of a series of questionnaires, and medical chart review. The questionnaires we use will be Beck Depression Inventory (BDI), Visual Analog Scale (VAS), McGill's short form, QoR-15 form and the Montgomery-Asberg Depression Rating Scale (MADRS). Please see below for a detailed discussion of these forms. In addition, from the chart review we will monitor length of stay during hospitalization, opioid usage per hour during the PACU stay before and after ketamine infusion, total opioid usage per day throughout the hospital stay, time to out of bed to chair, and spirometry use after ketamine infusion.

Specific aim 2: examine the effect of a single, subanesthetic dose (0.4mg/kg) of ketamine vs. saline control on inflammatory cytokines and neurotrophic factors in the postoperative period.

We will examine the effect of ketamine on proinflammatory markers and neurotrophic factors known to be linked with pain. We will examine levels of interleukin factor 1 and 6 (IL-1, IL-6), TNF- α , and BDNF. This aim will provide potential mechanism of action for ketamine.

Overall study design and plan

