An additional component of the study, which is entirely optional, is to obtain patient serum samples (about two teaspoons) in the operating room and 15 minutes and 4 hours after ketamine infusion. We will use these samples to assess levels of IL-1, IL-6, TNF- α , and BDNF, which are markers for pain. In addition, with patient consent, we will also store serum samples for future research use to measure other cytokines and neurotrophic factors and molecular markers associated with pain and depression.

Study site: Tisch Hospital

Outcome measures

Primary outcome measure: scores on the following questionnaires: 1) The Beck Depression Inventory (BDI); 2) Visual Analog Scale (VAS) score; 3) McGill's short form; 4) QoR-15 form; and 5) Montgomery-Asberg Depression Rating Scale (MADRS). The BDI and MADRS provide assessments for mood and function, VAS and McGill's assess pain, and QoR-15 assesses patient's overall satisfaction with postoperative recovery.

After consent is achieved in the pre-admission clinic prior to surgery, patients will be asked to fill out BDI, MADRS and QoR-15 forms to establish baseline scores. The BDI, MADRS will be filled out on postoperative days (POD) 0 after the infusion of ketamine, and BDI, MADRS and QoR-15 forms will be repeated on POD1, 2 and 7. McGill's short form will be filled out prior to discharge from the PACU and on POD 1, 2 and 7. VAS will be filled prior to PACU discharge, and every day while patient is in the hospital and on POD 7. VAS is a routine part of hospital care and will be administered daily whether a patient is enrolled in the study or not. If a patient has been discharged prior to POD2 or 7 (patients typically are discharged on POD2 or 3 in our practice), then a member of the study team will contact the patient by telephone to fill out these questionnaires.

Secondary outcome measures: 1) length of stay during hospitalization; 2) opioid usage per hour during the PACU stay before and after ketamine infusion; 3) opioid usage per day throughout the hospital stay; 4) time to out of bed to chair (OOB); 5) spirometry use 4 hours after the termination of ketamine infusion; 5) anti-emetic use in the PACU.

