Sample Size Justification: Previous studies on the antidepressant effects of ketamine on depressed patients typically yield a mean difference in psychometric measures of 40%, with a standard deviation of roughly 40% as well. Power analysis yields $n = 50$ patients in each arm. This will allow for us to detect a true difference in the mean value of our outcome variable of $\pm 22.5\%$ with a probability (power) of 0.8. The type I error probability associated with this test of the null hypothesis that the population means of the ketamine versus control groups are equal is 0.05.

Statistical Analysis

For this study, descriptive statistics will be performed for all data and subgroups as needed:

- 1) Outcome tests (see above), N (%) for each category, showing absolute values, absolute and percent differences, stratified by treatment etc.
- 2) Demographics showing continuous parameters (age, height, weight, etc.) as mean + SD; categorical parameters, as N (%); all also stratified by treatment.

Analysis of variance (ANOVA) test with repeated measures will be performed to determine within-patient effects (time) and between patient effects (treatment) on outcome measures. Pearson correlation will be used to assess relationships between continuous variables, and Spearman's Rho will be used for ranked data. For non-normally distributed data, the Kruskal-Wallis test will be used for global significance and Mann Whitney for subsequent pairwise comparisons.

Exploratory analysis will fit continuous (VAS score, length of stay in the hospital) and categorical (ordinal outcome data) to a Logistic Regression model which predicts the treatment bivariate (IV ketamine or placebo).

Interim Data analysis

An interim data analysis will be performed after a total of 50 patients have completed the study.

An analysis of primary and secondary endpoints will be analyzed, and if the primary endpoints are met, we will opt to terminate the study.

Data Safety and Monitoring Board (DSMB)

In addition to the PI, [name], an independent patient safety DSMB panel will also review study documents and safety data on a routine basis. This board will meet once every three months, and more frequently as needed. In addition, the board will meet with study coordinator and assistant after a total of 50 patients have completed the study to perform an interim analysis. This board will include the additional following members from the department of anesthesiology.

1. [name]
2. [name]

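### The repeated-measures ANOVA pre-specifies only time and treatment effects; treatment-by-time and a POD7 between-arm contrast are not planned, although a long-lasting effect is hypothesised

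*Combined protocol and SAP*

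**What the plan says.** The analysis sentence appears twice in the combined protocol and SAP, under Statistical Analysis and again in the Data Safety and Monitoring Plan: "Analysis of variance (ANOVA) test with repeated measures will be performed to determine within-patient effects (time) and between patient effects (treatment) on outcome measures". The fallback is rank-based and tied to no visit: "For non-normally distributed data, the Kruskal-Wallis test will be used for global significance and Mann Whitney for subsequent pairwise comparisons".

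On duration, the Background says of ketamine analgesia that "it is generally believed to be short lived, as the medication is metabolized within an hour", and of mood that "ketamine has rapid-onset antidepressant effects that may last up to seven days". The Study Rationale then says that ketamine given for postoperative pain "can be hypothesized to have long lasting analgesic effects as well as effects on improving mood and function in the postoperative period".

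The schedule is under Outcome measures. Before surgery, "patients will be asked to fill out BDI, MADRS and QoR-15 forms to establish baseline scores". The two mood scales are then completed on POD0 once the infusion is over, and both of them, together with QoR-15, follow on POD1, POD2 and POD7. The McGill short form is completed before PACU discharge and on POD1, 2 and 7. VAS is recorded before PACU discharge, daily in hospital and on POD7. Patients already discharged are contacted by telephone. All five questionnaires are listed as primary, with no primary time point.

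**The concern.** The trial collects data out to POD7, and a long-lasting effect is part of its rationale. Neither of the two named effects addresses that:

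- The time effect describes how both arms together change after surgery. It carries no information about ketamine.
- The treatment effect is a single between-arm difference averaged over the visits in the model. It equals the difference on a given day only if the effect is the same on every day.

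Two things are at stake. An effect confined to the first visit or two is diluted and may be missed. In the other direction, a significant treatment effect does not tell the reader whether any difference remained at POD7, because early visits alone can produce it.

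**Working it through.** **Inputs from the documents.** Difference 22.5%, SD 40%, 50 per arm, 1:1 allocation, alpha 0.05 (taken as two-sided because the difference is given as plus or minus), power 0.8.

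**Assumptions not in the documents.** The 40% SD applies at each visit. Within-patient correlation ρ is 0.3 to 0.7 and equal between all pairs of visits. The effect is either 22.5% or zero at each visit.

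**Step 1: the plan's own figure.** n per arm = 2 × (1.96 + 0.842)² × (40/22.5)² = 49.6, so 50. Power with 50 per arm is 0.803 by the normal approximation and 0.795 by the t-test. The stated sample size reproduces, but it is for one comparison of two means, not for a visit average.

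**Step 2: the treatment main effect over four post-infusion visits.** This structure fits BDI and MADRS (POD0, 1, 2, 7) and McGill (PACU, POD1, 2, 7). With an effect at m of 4 visits:

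- averaged difference = 22.5 × m/4
- SD of a patient's mean over visits = 40 × √((1 + 3ρ)/4), which is 27.6 at ρ = 0.3, 31.6 at 0.5 and 35.2 at 0.7
- noncentrality = averaged difference / (SD × √(2/50)), t-test on 98 df

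For example, with m = 1 and ρ = 0.5 the noncentrality is 5.625 / (31.6 × 0.2) = 0.89, and power is 0.14.

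| Visits with effect | Averaged difference | ρ = 0.3 | ρ = 0.5 | ρ = 0.7 |
|---|---|---|---|---|
| 4 of 4 | 22.5% | 0.98 | 0.94 | 0.89 |
| 3 of 4 | 16.9% | 0.86 | 0.75 | 0.66 |
| 2 of 4 | 11.25% | 0.52 | 0.42 | 0.35 |
| 1 of 4 | 5.6% | 0.17 | 0.14 | 0.12 |

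A direct comparison on one day when the effect is present has power 0.80 (Step 1).

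**Step 3: baseline kept as a fifth level of time.** The plan does not say how baseline is handled for BDI and MADRS. If it is a level of time, an effect constant at all four post-infusion visits averages to 22.5 × 4/5 = 18%, with SD 40 × √((1 + 4ρ)/5), and power is 0.92, 0.82 and 0.72 for ρ = 0.3, 0.5 and 0.7. The same sustained effect has 0.98 to 0.89 when baseline is left out.

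**Step 4: what the interaction test adds.** On post-infusion visits only, the treatment-by-time F test has power 0.68 to 0.97 (ρ = 0.3 to 0.7) when the effect is at one of four visits. When the effect is equal at all four, it rejects only 5% of the time, which is alpha. It detects a changing effect, but it cannot establish a lasting one. Only a between-arm contrast at a late visit does that.

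**The case against.** A two-factor repeated-measures ANOVA routinely outputs the interaction, so the sentence may be shorthand for a fuller model. That stands in part: a reader might infer that duration will never be examined, and the documents do not support that. What they support is that neither the interaction nor a late contrast is pre-specified. With five primary questionnaires and an option to stop at 50 patients if the primary endpoints are met, results picked from software output afterwards would be weak evidence.

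The average is a legitimate target, since the stated null is equal means in the two arms. If the mood effect does last through POD7, averaging over post-infusion visits is more powerful than a single day (0.98 to 0.89 against 0.80). This also stands, and the average should be kept. It is also true that Specific aim 1 mentions no duration and that the long-lasting claim is one sentence of rationale. Even so, the late visit is scheduled and has no planned test of its own.

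An early effect is not left to the questionnaire average alone. PACU opioid use before and after infusion, daily opioid use and spirometry at 4 hours are secondary outcomes. The planned descriptive differences, or the Mann-Whitney comparisons, could be made by visit, but the text does not say so.

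It would be too strong to say that a short-lived effect is averaged away. It is diluted, to a quarter of its size for one visit in four. Nor do the documents say that a significant main effect will be reported as a lasting one. With a real effect at POD0 to POD2 only, rejecting equal means is correct, and the error would lie in the interpretation.

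**Conclusion.** The point holds as a gap in pre-specification. As written, the plan names a treatment effect that dilutes a fading effect and cannot show a difference at POD7, and it names nothing that can. With an effect at one or two of four post-infusion visits, power of that main effect is 0.12 to 0.52, against 0.80 for a comparison on a day when the effect is present. An effect at three of the four gives a significant main effect 66% to 86% of the time whether or not POD7 is one of them.

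The exact figures depend on the assumed correlation, equal correlations between visits, on/off effects and the treatment of baseline. The dilution has the same direction over the whole range. The four-visit figures do not carry over to QoR-15, which has three postoperative visits and no POD0 form, or to VAS, whose number of in-hospital days varies with length of stay. This should be changed. It is a modest revision of the analysis, and it does not invalidate the averaged comparison.

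**What to change.** Make the same change in both copies of the Statistical Analysis text.

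- **Model.** For each questionnaire, fit treatment, time and treatment-by-time, with post-infusion visits as categories: BDI and MADRS at POD0, 1, 2 and 7; McGill at PACU, POD1, 2 and 7; QoR-15 at POD1, 2 and 7; VAS at PACU, in-hospital days and POD7.
- **Baseline.** Use the baseline score as a covariate, not a level of time, where it is collected (BDI, MADRS, QoR-15).
- **Estimates.** Report the ketamine-minus-placebo difference with 95% CI at each visit, alongside the average over visits.
- **Lasting effect.** State that any such claim rests on the POD7 difference, not on the treatment main effect or the interaction test.
- **Multiplicity.** Declare the other per-visit differences descriptive, or adjust them for multiplicity.

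The cost is wording and one model term, with no new visits, patients or data. Two downsides should be acknowledged. Per-visit estimates are less precise than the average. There are also more comparisons: 4 + 4 + 4 + 3 = 15 for BDI, MADRS, McGill and QoR-15, and about 19 if VAS contributes roughly four.

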This is a randomized, double-blind, placebo-controlled, two-arm parallel, single-center study. One hundred subjects (50 in each arm) will be enrolled. Subjects, between the ages 18 and 65, undergoing laparoscopic gastric bypass or sleeve gastrectomy under general anesthesia will be screened for eligibility to participate in the study. Subjects will be screened, recruited and consented during the preadmission visit prior to surgery. Eligible subjects will be randomized to one of the two treatment group in a 1:1 ratio to receive either IV ketamine (0.4mg/kg) or matching placebo. Both men and women will be recruited, and there is no limitation as to racial and ethnic origin.

Participation in the study will not alter the patient's surgical or anesthetic care, post-anesthetic care, or care on the floor. In the PACU, patients, if deemed medically stable by the study physician, will receive either 0.4mg/kg IV ketamine or placebo. All patients will also receive standard post-anesthetic monitoring and care, as well as routine care after transfer out of the PACU. There is no restriction on the use of other analgesics throughout the hospital stay. Patients are followed until the date of discharge, and endpoints (see below) are collected from patient reports as well as from medical charts. During their hospital stay (and once after their discharge from the hospital), patients will fill out five questionnaires which provide estimates of their postoperative pain control, mood and function, and quality of postsurgical recovery.

Patients will be randomized using a block randomization code for assigning 100 subjects to two groups. In Excel we generated 100 random numbers. In the next column we inserted multiple copies of the sequence PCPC where p= "placebo" and c = "control", forming 25 blocks. Then we sorted the random numbers in each 4 subject block, including the assignment letters (P, C) in the sort. The remaining list of Ps and Cs is the randomization.

To check the balance, we then did running counts of the cumulative repeats of "p" and "c" and "p - c". The tally for each totaled 50 and the two groups were always within 2 counts of being perfectly balanced, which met our goal. The list can be extended at will to accommodate screening failures.

Randomization lists will be sent to the pharmacy who will then be able to distribute the study drug/placebo as patients are enrolled and undergoing surgery, and the remainder of the study staff will be blinded.

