Sample Size Justification: Previous studies on the antidepressant effects of ketamine on depressed patients typically yield a mean difference in psychometric measures of 40%, with a standard deviation of roughly 40% as well. Power analysis yields $n = 50$ patients in each arm. This will allow for us to detect a true difference in the mean value of our outcome variable of $\pm 22.5\%$ with a probability (power) of 0.8. The type I error probability associated with this test of the null hypothesis that the population means of the ketamine versus control groups are equal is 0.05.

Statistical Analysis: For this study, descriptive statistics will be performed for all data and subgroups as needed:

- 1) Outcome tests (see above), N (%) for each category, showing absolute values, absolute

and percent differences, stratified by treatment etc.

- 2) Demographics showing continuous parameters (age, height, weight, etc.) as mean + SD; categorical parameters, as N (%); all also stratified by treatment.

Analysis of variance (ANOVA) test with repeated measures will be performed to determine within-patient effects (time) and between patient effects (treatment) on outcome measures. Pearson correlation will be used to assess relationships between continuous variables, and Spearman's Rho will be used for ranked data. For non-normally distributed, the Kruskal-Wallis test will be used for global significance, and Mann Whitney for subsequent pairwise comparisons.

Exploratory analysis will fit continuous (VAS score, length of stay in the hospital) and categorical (ordinal outcome data) to a Logistic Regression model which predicts the treatment bivariate (IV ketamine or placebo).

Interim Data analysis: An interim data analysis will be performed after a total of 50 patients have completed the study. An analysis of primary and secondary endpoints will be analyzed, and if the primary endpoints are met, we will opt to terminate the study.

DATA SAFETY AND MONITORING PLAN

Timeline

- 1) Estimated start date: Sept 1, 2013
- 2) Estimated time for start-up: 2 months
- 3) Time allotted for enrollment: 2 years
- 4) Estimated study end date: August 30, 2015

Data acquisition and management

The research material obtained from human subjects in this proposed study will be collected solely for research purposes. It will be as follows:

- a. *Clinical information* obtained by medical history, questionnaires and interviews.

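### With two arms, the non-normal fallback (Kruskal-Wallis, then Mann-Whitney) is a single test and does not replace the repeated-measures ANOVA for the five repeated primary scores

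*Combined protocol and SAP*

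**What the plan says.** The design, under Overall study design and plan, is a "two-arm parallel, single-center study", with patients allocated "in a 1:1 ratio to receive either IV ketamine (0.4mg/kg) or matching placebo".

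Under Outcome measures, all five questionnaires are primary and all are repeated after the infusion:
- BDI and MADRS: postoperative days 0, 1, 2 and 7 (four scores).
- McGill short form: before PACU discharge and on days 1, 2 and 7 (four scores).
- QoR-15: days 1, 2 and 7 (three scores).
- VAS: before PACU discharge, daily in hospital and on day 7 (a number that varies with length of stay).

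The main analysis is a repeated-measures ANOVA with a within-patient effect of time and a between-patient effect of treatment. The fallback is then given as: "For non-normally distributed data, the Kruskal-Wallis test will be used for global significance and Mann Whitney for subsequent pairwise comparisons". The Statistical Analysis text appears twice, once before and once inside the Data Safety and Monitoring Plan. The other copy agrees: "the Kruskal-Wallis test will be used for global significance, and Mann Whitney for subsequent pairwise comparisons".

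Neither copy says which groups are compared, at which visit, on raw scores or changes, what the pairs are, how several visits are adjusted for, or what makes data count as non-normal.

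**The concern.** A global test followed by pairwise tests presupposes at least three groups, and this trial has two arms. For repeated scores, three or more groups can only be visits or arm-by-visit cells. Those hold several scores from the same patient, while both tests assume independent observations.

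The fallback may well be used. Eligibility sets no minimum depression score, so BDI and MADRS could pile up near the floor. With no rule for declaring non-normality, the switch and the form of the test could be settled after the data are seen. The stakes include the interim analysis after 50 completed patients, where the trial may stop if the primary endpoints are met.

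**Working it through.** **1. The plan's own figure.** Inputs are a detectable difference of 22.5%, "with a standard deviation of roughly 40% as well", power 0.80 and alpha 0.05, taken as two-sided.

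n per arm = 2 × (1.96 + 0.8416)² × (40/22.5)² = 2 × 7.849 × 3.160 = 49.6, rounded up to 50.

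This agrees with "Power analysis yields $n = 50$ patients in each arm". The formula compares one value per patient between arms, so this point leaves the sample size unaffected.

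**2. Two arms, one test.** With two groups the Kruskal-Wallis statistic is the square of the Mann-Whitney z without continuity correction, referred to chi-square on 1 degree of freedom. On one simulated data set of 50 per arm both gave p = 0.8577. No pairwise step is left to take.

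**3. What each reading does when ketamine has no effect.** From the plan: 50 per arm, and four post-infusion scores (as for BDI, MADRS and McGill). Assumed, because the documents give no figures: skewed (lognormal) scores, and a within-patient correlation on the log scale of 0.3, 0.5 or 0.7, with 0 as a check. The table gives the proportion of simulated trials with p < 0.05. There were 4,000 trials per entry (1,000 for the drift row). The Monte Carlo standard error near 0.05 is √(0.05 × 0.95/4000) = 0.003.

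| Reading of the rule | 0 | 0.3 | 0.5 | 0.7 |
|---|---|---|---|---|
| Arms compared at each visit, any of four significant | 0.186 | 0.175 | 0.143 | 0.130 |
| All scores pooled by arm | 0.044 | 0.146 | 0.200 | 0.259 |
| Kruskal-Wallis on 8 arm-by-visit cells, no change over time | 0.052 | 0.034 | 0.032 | 0.042 |
| Same 8 cells, same drift in both arms (0.3 SD per visit, assumed) | 1.00 | 1.00 | 1.00 | 1.00 |
| Arms compared at one named visit | 0.048 | 0.045 | 0.052 | 0.049 |
| Arms compared on each patient's mean of four scores | 0.044 | 0.045 | 0.043 | 0.043 |

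**4. Checks by hand.**
- Any of four independent visits: 1 − 0.95⁴ = 0.185, against 0.186 simulated at correlation 0. For the three QoR-15 visits the independent figure is 1 − 0.95³ = 0.143.
- Pooled scores: variance inflation is 1 + 3ρ = 1.9, 2.5 and 3.1. True size is 2 × [1 − Φ(1.96/√inflation)] = 0.155, 0.215 and 0.266, close to the simulated row.
- Cells: with a smaller assumed trend (0.6 SD falling to 0, the same in both arms), the 8-cell test still rejects in 92% of 1,000 trials. It is responding to time, not treatment.

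**5. Power of one value per patient.** At the design effect of 22.5/40 = 0.5625 SD with normal scores, Mann-Whitney at one visit has power of about 0.77, against 0.80 for the z-test. On the patient mean, with the same effect at all four visits, power is 0.97, 0.93 and 0.87 at correlations 0.3, 0.5 and 0.7. Keeping the patient as the unit need not cost power.

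**The case against.** The best defence is that the sentence is generic wording, tied to no outcome and placed after a list of correlation methods. It most naturally means comparing the arms, visit by visit or on outcomes with a single value. Under that meaning each Mann-Whitney test is a valid randomised comparison, the main ANOVA is still stated, and naming the groups and visits would settle the matter.

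Much of this stands, and it rules out three stronger readings:
- A reader might infer that the plan treats a patient's repeated scores as independent. The documents never say that visits are pooled or used as groups. The pooled and cell-wise figures show what the wording permits, not what it prescribes.
- A reader might infer that the fallback gives no valid treatment test. It does at one named visit, on a per-patient summary, or on length of stay or time to out of bed.
- A reader might infer that the inflation favours ketamine. Under no effect a two-sided test errs equally in both directions, so about half of the false positives would favour placebo.

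Skewness is also presumed, since the documents report no score distributions. The cell-wise result depends on the assumed recovery trend; with none, the test rejects in only 3 to 4% of trials at correlations 0.3 to 0.7.

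The defence does not rescue the rule for repeated outcomes. Even its most natural reading leaves several unadjusted visits per score and drops the repeated-measures structure.

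**Conclusion.** The concern holds in a limited form. For the arm comparison the two-step rule is empty. For the five repeated primary scores it is no substitute for the repeated-measures ANOVA, because it has no within-patient term and cannot express treatment by time.

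This is more than missing detail, because each of the readings examined for the full set of repeated scores is worse than the analysis it would replace. For a four-visit score at assumed correlations of 0.3 to 0.7, false-positive rates are about 0.13 to 0.175 if any unadjusted visit may count, and about 0.15 to 0.26 if scores are pooled by arm. The cell-wise test mostly reports recovery over time.

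These rates are for one score at 50 per arm. They exclude the multiplicity of five primary scores and of the interim look. The four-visit rates do not carry over directly to QoR-15 (three visits) or VAS (a varying number).

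**What to change.** Replace the fallback sentence in both copies of the Statistical Analysis section with a rule for each type of outcome.

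- **One value per patient** (such as length of stay and time to out of bed): Mann-Whitney between arms, with a Hodges-Lehmann difference and 95% CI.
- **Repeated outcomes:** keep the repeated-measures model whatever the distribution. Take the treatment p-value from a re-randomisation test that reassigns arm within the randomisation blocks of four, and the 95% CI from a bootstrap that resamples whole patients. State that the p-value decides if the two disagree near the boundary. No normality rule is then needed.
- **One pre-named treatment contrast per outcome**, so that no unadjusted per-visit test decides the result. For VAS, list the time points that enter, because the number of in-hospital scores depends on length of stay.

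Fix the method for each outcome before unblinding, including before the interim analysis at 50 patients. The cost is SAP wording and a little more programming, with no additional patients, visits or data.
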